9.4.2 Duration of Remission and Relapse-free Survival for Patients Having Complete Remission

Duration of complete remission is defined as the interval from the date that complete remission is documented to the date of recurrence, death due to any cause, or loss to follow-up.

Relapse-free survival is defined only for those patients achieving a complete remission. It is defined as the interval from the date of first documentation of a leukemia-free state to the date of recurrence, death due to any cause, or loss to follow up.

9.4.3 Safety

Safety evaluation will include assessments of adverse experiences, medical history, physical examinations, vital signs, and laboratory assessments at baseline and throughout the study period. Local laboratories may be used for this study.

10.0 ADVERSE EVENT REPORTING

10.1 Adverse Events (AEs)

Definition: any unfavorable medical occurrence in a human subject including any abnormal sign, symptom, or disease.

Grading: the descriptions and grading scales found in the revised NCI Common Terminology Criteria for Adverse Events (CTCAE) version 4.0 will be utilized for all toxicity reporting. A copy of the CTCAE version 4.0 can be downloaded from the CTEP web site: <http://ctep.cancer.gov/reporting/ctc.html>. Grade 1-2 events will be recorded for the first fifty enrolled patients. Subsequently, only events graded as 3 or greater will be recorded. Fifty patients should be sufficient to estimate the true incidence of any adverse event to within $\pm 14\%$ with 95% confidence intervals.

Attribution (relatedness), Expectedness, and Seriousness: the definitions for the terms listed that should be used are those provided by the Department of Health and Human Services' Office for Human Research Protections (OHRP). A copy of this guidance can be found on OHRP's website: (<http://www.hhs.gov/ohrp/policy/AdvEvtGuid.htm>).

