14.0 STATISTICAL ANALYSIS METHODS AND SAMPLE SIZE

14.1 Analysis Populations

Intent-to-Treat - The intent-to-treat (ITT) population will be defined as all patients who receive at least one dose of decitabine.

Efficacy-Evaluable - The efficacy-evaluable (EE) population will be defined as all patients who receive at least one cycle of treatment.

Safety - The safety population will be defined as all patients with at least one dose of decitabine.

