14.2.4 Safety Analysis

Extent of Exposure – Duration (number of cycles/infusions) of decitabine doses (cumulative and intensity) will be summarized.

Adverse Events - All adverse events will be coded using NCI CTCAE v. 4.0. The incidence of treatment-emergent adverse events (number and percent of patients reporting the adverse event at least once during the study) will be summarized. In addition, adverse events will be summarized by investigator attribution of relationship to study medication and by grade. Similar summaries will be provided by treatment cycle.

Clinical Laboratory Evaluation – Applicable laboratory parameters will be graded according to NCI CTCAE version 4.0. The incidence of maximum grade (number and percent of patients experiencing the maximum grade during the study) will be summarized for each laboratory parameter. Similar summaries will be provided by treatment cycle. Graphical displays of select hematological parameters will also be provided.

Vital Signs, Physical Findings, and Other Safety Observations – Vital signs, findings from physical examinations, ECOG scores and weights will be presented in listing format.

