14.3 Sample Size

We anticipate initially enrolling 25 patients at Washington University. Once we establish a routine exome analysis with validation and calculation of the rate of patient-specific mutation clearance, we will enroll an additional 100 patients from at least 2 additional centers.

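### Grade 1-2 adverse events are recorded only in the first 50 enrolled patients, but section 14.2.4 gives low-grade and any-grade incidence no denominator of its own

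*Combined protocol and SAP*

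**What the plan says.** The file holds several full protocol versions. This point concerns the one with the multicentre text (12.0 Auditing, 13.0 Multicenter Regulatory Requirements) and its statistics in section 14.0.

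- **Collection (10.1).** "Grade 1-2 events will be recorded for the first fifty enrolled patients. Subsequently, only events graded as 3 or greater will be recorded". The section supports the rule by stating that fifty patients give a 95% confidence interval of about ±14 percentage points for any event's incidence.
- **Population (14.1).** "The safety population will be defined as all patients with at least one dose of decitabine". No other safety set is defined.
- **Analysis (14.2.4).** "The incidence of treatment-emergent adverse events (number and percent of patients reporting the adverse event at least once during the study) will be summarized". Breakdowns by attributed relationship to the drug, by grade and by cycle are also planned. No denominator is named, and the first-50 rule is not mentioned.
- **Size (14.3).** "We anticipate initially enrolling 25 patients at Washington University", followed by a further 100 from at least two other centres. Section 14.2.2 also gives 125 as the number enrolled.

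**The concern.** The collection rule and the analysis text do not fit together. After the fiftieth enrolment a patient can have a grade 1-2 event that the database will never hold. If that patient stays in the denominator, the event counts as not having occurred. With 125 dosed this applies to 125 − 50 = 75 patients.

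It looks like an amendment that was only partly carried through. The other versions shown have their statistics in section 12.0 and have no first-50 rule, and their safety analysis text (12.2.4) is the same as 14.2.4 here. The row on cumulative events for the monitoring report was adapted: those versions ask for events of every grade, whereas 10.10 here no longer mentions grade. The analysis section was left as it was.

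At stake is the descriptive safety profile. The error runs one way, towards too little low-grade toxicity, and it grows with each patient dosed after the first 50. Any-grade tables would also combine two collection rules without saying so.

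**Working it through.** **Inputs**

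- Patients with grade 1-2 events recorded: 50 (10.1).
- Planned enrolment: 25 + 100 = 125 (14.3; also 14.2.2).
- Number dosed, N: the documents give no figure beyond the plan, so a range of 100 to 125 is assumed.
- Event incidences: not in the documents. All values of p and q below are illustrations.
- It is also assumed that all of the first 50 enrolled are dosed, and that true incidence is the same before and after patient 50.

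**Step 1: the plan's own precision figure.** Half-width at the worst case of 50% incidence with n = 50:

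1.96 × √(0.5 × 0.5 / 50) = 0.1386, or 13.9 percentage points.

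This reproduces the stated ±14. At 25/50 a Wilson interval gives ±13.4 points and an exact interval ±14.5. The figure is correct, and it belongs to a denominator of 50.

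**Step 2: grade 1-2 incidence.** With true incidence p, the expected number of patients with a recorded event is 50p. On all dosed patients the reported rate is 50p/N, so the understatement factor is p ÷ (50p/N) = N/50.

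| N dosed | Factor | True 30% reported as | True 60% reported as |
|---|---|---|---|
| 125 | 2.5 | 12% | 24% |
| 120 | 2.4 | 12.5% | 25% |
| 110 | 2.2 | 13.6% | 27.3% |
| 100 | 2.0 | 15% | 30% |

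**Step 3: any-grade incidence.** Let p be the share of patients with grade 1-2 only and q the share with grade 3 or higher. The true rate is p + q. The reported rate is (50/N)p + q, because grade 3 or higher events are recorded in everyone. With N = 125, 50/N = 0.4:

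| p | q | True | Reported | Factor |
|---|---|---|---|---|
| 40% | 0% | 40% | 0.4 × 40 + 0 = 16% | 2.50 |
| 40% | 5% | 45% | 0.4 × 40 + 5 = 21% | 2.14 |
| 40% | 10% | 50% | 0.4 × 40 + 10 = 26% | 1.92 |
| 30% | 20% | 50% | 0.4 × 30 + 20 = 32% | 1.56 |
| 10% | 80% | 90% | 0.4 × 10 + 80 = 84% | 1.07 |

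The factor equals N/50 only when there are no grade 3 or higher cases, and it approaches 1 as severe cases dominate. For grade 3 or higher alone it is exactly 1.

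**Step 4: is the gap large against sampling error?** Take 20 patients with a recorded low-grade event, all among the first 50. On 50 the rate is 40% (exact 95% interval 26% to 55%). On 125 it is 16% (10% to 24%). The second interval excludes the rate seen where the event was actually recorded.

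**The case against.** The strongest reply is that 14.2.4 names no denominator. The use of all dosed patients is inferred from 14.1, and the precision sentence in 10.1 shows that the authors meant to estimate from fifty. A careful statistician reading both sections might use fifty for low-grade events without being told. That is a fair account of intent. But the intended denominator never reaches the analysis section, the only safety set defined is the full one, and the two readings differ by up to 2.5-fold. A point of that size should not be left to the analyst.

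Three limits on scope also stand:

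- **Laboratory grades.** 14.2.4 summarises maximum laboratory grade separately. Blood counts and chemistries are scheduled for every patient (5.2.3, 5.2.7, 5.2.8), so grades derived from those values are not affected.
- **Consequences.** The safety analysis is descriptive, and no test or stopping rule in the text shown depends on grade 1-2 incidence. A reader might infer that the plan will make the 10-day schedule look safer than the 5-day historical controls. The documents do not support that: the historical comparison in 14.2.3 concerns response rates only.
- **Versions.** The file is the second of two parts and opens with the end of another version's reference list. A corrected 14.2.4 in the part not shown cannot be excluded.

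**Conclusion.** The point holds as an unreconciled conflict between 10.1 and 14.2.4 in this version. Applied as written, with the one safety set that is defined, the plan understates grade 1-2 incidence by N/50: 2.5-fold with all 125 dosed, 2.0-fold with an assumed 100. It understates any-grade incidence by a factor between 1 and N/50, depending on the share of severe cases.

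Three stronger readings are tempting and should not be adopted. The first is that the plan expressly commits to 125 as the denominator for low-grade events; it is silent, and 125 follows only by joining 14.1 with 14.3. The second is that all reported toxicity is diluted 2.5-fold; that figure needs every enrolled patient to be dosed and applies only to grade 1-2 rates and to events with no grade 3 or higher cases. The third is that the ±14 points are wrong; they are right for 50 patients and simply do not describe a rate computed on 125.

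The decision to stop recording low-grade events after fifty patients is not in question, and the primary analysis is untouched.

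**What to change.** Amend 14.2.4 to say:

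- Grade 1-2 and any-grade adverse event incidence (overall, by attribution and by cycle) uses dosed patients among the first 50 enrolled, for numerator and denominator alike. The word dosed matters: 10.1 counts enrolled patients while 14.1 requires a dose, so the subset may be slightly under 50.
- Grade 3 or higher incidence uses the full safety population.
- Each table states its denominator.

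The cost is about one sentence and two table denominators, with no new data. The small downside is that low-grade and any-grade rates then rest on about 50 patients, with the ±14-point precision that 10.1 already accepts. If a later version already contains this, no change is needed.

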10.2 Unanticipated Problems

Definition:

- unexpected (in terms of nature, severity, or frequency) given (a) the research procedures that are described in the protocol-related documents, such as the IRB-approved research protocol and informed consent document; and (b) the characteristics of the subject population being studied;
- related or possibly related to participation in the research (in this guidance document, possibly related means there is a reasonable possibility that the incident, experience, or outcome may have been caused by the procedures involved in the research); and
- suggests that the research places subjects or others at a greater risk of harm (including physical, psychological, economic, or social harm) than was previously known or recognized.

10.3 Noncompliance

Definition: failure to follow any applicable regulation or institutional policies that govern human subjects research or failure to follow the determinations of the IRB. Noncompliance may occur due to lack of knowledge or due to deliberate choice to ignore regulations, institutional policies, or determinations of the IRB.

10.4 Serious Noncompliance

Definition: noncompliance that materially increases risks, that results in substantial harm to subjects or others, or that materially compromises the rights or welfare of participants.

10.5 Protocol Exceptions

Definition: A planned deviation from the approved protocol that are under the research team's control. Exceptions apply only to a single participant or a singular situation.

Local IRB Pre-approval of all protocol exceptions must be obtained prior to the event. For secondary sites, the Washington University PI will issue approval of the exception, but it must also be submitted to the local IRB with documentation of approval forwarded to Washington University. HRPO approval is not required for protocol exceptions occurring at secondary sites.

10.6 Reporting to the Human Research Protection Office (HRPO) and the Quality Assurance and Safety Monitoring Committee (QASMC) at Washington University:

The PI is required to promptly notify the IRB of the following events:

- Any unanticipated problems involving risks to participants or others which occur at WU, any BJH or SLCH institution, or that impacts participants or the conduct of the study.
- Noncompliance with federal regulations or the requirements or determinations of the IRB.
- Receipt of new information that may impact the willingness of participants to participate or continue participation in the research study.

These events must be reported to the IRB within **10 working days** of the occurrence of the event or notification to the PI of the event. The death of a research participant that qualifies as a reportable event should be reported within **1 working day** of the occurrence of the event or notification to the PI of the event.

10.7 Reporting Requirements for Secondary Sites

The research team at each secondary site is required to promptly notify the Washington University PI and research coordinator of all reportable events (as described in Section 7.6) within **1 working day** of the occurrence of the event or notification of the secondary site's PI of the event. This notification may take place via email if there is not yet enough information for a formal written report (using either an FDA MedWatch form if required or an institutional SAE reporting form if not). A formal written report must be sent to the Washington University PI and research coordinator within **10 working days** of the occurrence of the event or notification of the secondary site's PI of the event. The death of a research participant that qualifies as a reportable event should be reported within **1 working day** of the occurrence of the event or notification of the secondary site's PI of the event.

The research team at a secondary site is responsible for following its site's guidelines for reporting applicable events to its site's IRB according to its own institutional guidelines.

10.8 Reporting to Secondary Sites

The Washington University PI (or designee) will notify the research team at each secondary site of all reportable events that have occurred at other sites (as described in Section 7.6) within **10 working days** of the occurrence of the event or notification of the PI of the event. This includes events that take place both at Washington University and at other secondary sites, if applicable.

10.9 Reporting to the FDA

The conduct of the study will comply with all FDA safety reporting requirements. **PLEASE NOTE THAT REPORTING REQUIREMENTS FOR THE FDA DIFFER FROM REPORTING REQUIREMENTS FOR HRPO/QASMC.** It is the responsibility of the investigator to report any unanticipated problem to the FDA as follows:

- Report any unexpected fatal or life-threatening adverse experiences associated with use of the drug (i.e., there is a reasonable possibility that the experience may have been caused by the drug) by telephone or fax no later than **7 calendar days** after initial receipt of the information. A life-threatening adverse experience is defined as any adverse drug experience that places the subject (in the view of the investigator) at immediate risk of death from the reaction as it occurred, i.e., it does not include a reaction that, had it occurred in a more severe form, might have caused death.
- Report any serious, unexpected adverse experiences, as well as results from animal studies that suggest significant clinical risk within **15 calendar days** after initial receipt of this information. A serious adverse drug experience is defined as any adverse drug experience occurring at any dose that results in any of the following outcomes:
 - Death
 - A life-threatening adverse drug experience
 - Inpatient hospitalization or prolongation of existing hospitalization
 - A persistent or significant disability/incapacity (i.e., a substantial disruption of a person's ability to conduct normal life functions)
 - A congenital anomaly/birth defect
 - Any other experience which, based upon appropriate medical judgment, may jeopardize the subject and may require medical or surgical intervention to prevent one of the outcomes listed above

An unexpected adverse drug experience is defined as any adverse drug experience, the specificity or severity of which is not consistent with the current investigator brochure (or risk information, if an IB is not required or available).

All MedWatch forms will be sent by the investigator or investigator’s team to the FDA at the following address or by fax:

Food and Drug Administration
 Center for Drug Evaluation and Research
 Division of Oncology Drug Products
 [name]
 [name]
 FAX: [name]

Secondary sites must submit a completed MedWatch form to the Washington University PI and research coordinator within **4 calendar days** (for fatal or life-threatening adverse experiences) or **11 calendar days** (for serious, unexpected adverse experiences). The Washington University PI will be responsible for submitting all MedWatch forms from secondary sites to the FDA within the timeframes specified above.

10.10 Timeframe for Reporting Required Events:

Reportable adverse events will be tracked for 30 days following the last day of study treatment, or until the start of a new chemotherapy/treatment, whichever comes first.

Deaths	
Any reportable death while on study or within 30 days of study	Immediately, within 24 hours, to PI and the IRB
Any reportable death while off study	Immediately, within 24 hours, to PI and the IRB
Adverse Events/Unanticipated Problems	
Any reportable adverse events as described in Sections 10.1 and 10.2 (other than death) and 10.7	Immediately, within 24 hours to PI and within 10 working days to the IRB, and within 7 or 15 days to the FDA
All adverse events are to be reported per protocol regardless of attribution should be submitted cumulatively	Include in DSM report
Noncompliance and Serious Noncompliance	
All noncompliance and serious noncompliance as described in Sections 10.3 and 10.4	Immediately, within 24 hours, to PI and within 10 working days to the IRB

11.0 DATA SAFETY MONITORING PLAN

In compliance with the Washington University Institutional Data and Safety Monitoring Plan, the Principal Investigator will provide a Data and Safety Monitoring (DSM) report to the Washington University Quality Assurance and Safety Monitoring Committee (QASMC) semi-annually beginning six months following activation of the first secondary site.

The Principal Investigator will review all patient data at least every six months, and provide a semi-annual report to the QASMC. This report will include:

- HRPO protocol number, protocol title, Principal Investigator name, data coordinator name, regulatory coordinator name, and statistician
- Date of initial HRPO approval, date of most recent consent HRPO approval/revision, date of HRPO expiration, date of most recent QA audit, study status, and phase of study
- History of study including summary of substantive amendments; summary of accrual suspensions including start/stop dates and reason; and summary of protocol exceptions, error, or breach of confidentiality including start/stop dates and reason
- Study-wide target accrual and study-wide actual accrual including numbers from participating sites
- Protocol activation date at each participating site
- Average rate of accrual observed in year 1, year 2, and subsequent years at each participating site
- Expected accrual end date and accrual by site
- Objectives of protocol with supporting data and list the number of participants who have met each objective
- Measures of efficacy
- Early stopping rules with supporting data and list the number of participants who have met the early stopping rules
- Summary of toxicities at all participating sites
- Abstract submissions/publications
- Summary of any recent literature that may affect the safety or ethics of the study

Until such a time as the first secondary site activates this protocol, a semi-annual DSM report to be prepared by the study team will be submitted to the QASM Committee beginning 6 months after study activation at Washington University.

The study principal investigator and Research Patient Coordinator will monitor for serious toxicities on an ongoing basis. Once the principal investigator or Research Patient Coordinator becomes aware of an adverse event, the AE will be reported to the HRPO and QASMC according to institutional guidelines.

12.0 AUDITING

Since Washington University is the coordinating center, each site will be audited annually by Siteman Cancer Center personnel (QASMC) unless the outside institution has an auditing mechanism in place and can provide a report. The outside sites will be asked to send copies of all audit materials, including source documentation. The audit notification will be sent to the Washington University Research Patient Coordinator, who will obtain the audit materials from the participating institution.

Notification of an upcoming audit will be sent to the research team one month ahead of the audit. Once accrual numbers are confirmed, and approximately 30 days prior to the audit, a list of the cases selected for review (up to 10 for each site) will be sent to the research team. However, if during the audit the need arises to review cases not initially selected, the research team will be asked to provide the additional charts within two working days.

Additional details regarding the Auditing Policies and procedures can be found at http://www.siteman.wustl.edu/uploadedFiles/Research_Programs/Clinical_Research_Resources/Protocol_Review_and_Monitoring_Committee/QASMCQualityAssurance.pdf

13.0 MULTICENTER REGULATORY REQUIREMENTS

Washington University requires that each participating site sends its informed consent document to be reviewed and approved by the Washington University Regulatory Coordinator (or designee) prior to IRB/IEC submission.

Each participating institution must have the following documents on file at Washington University prior to first subject enrollment:

- Documentation of IRB approval of the study in the form of a letter or other official document from the participating institution's IRB. This documentation must show which version of the protocol was approved by the IRB.
- Documentation of IRB approval of an informed consent form. The consent must include a statement that data will be shared with Washington University, including the Quality Assurance and Safety Monitoring Committee (QASMC), the DSMC (if applicable), and the Washington University study team.
- Documentation of FWA, signed FDA Form 1572, and signed and dated CVs of all participating investigators.
- Documentation of training in protection of human subjects by all participating investigators.
- Protocol signature page signed and dated by the investigator at each participating site.

The Principal Investigator is responsible for disseminating to the participating sites all study updates, amendments, reportable adverse events, etc. There will be one current version of the protocol document at any given time and each participating institution will utilize that document. Protocol/consent modifications and IB updates will be forwarded electronically to the secondary sites within 2 weeks of obtaining Washington University IRB approval with acknowledgement of receipt requested. Secondary sites are to submit protocol/consent/IB modifications to their local IRBs within 4 weeks of receipt, and confirmation of submission must be forwarded to the appropriate contact person on the Washington University study team at the time of submission. Upon the secondary sites obtaining local IRB approval, documentation of such shall be sent to the Washington University study team within 2 weeks of receipt of approval.

Documentation of participating sites' IRB approval of annual continuing reviews, protocol amendments or revisions, all SAE reports, and all protocol violations/deviations/exceptions must be kept on file at Washington University.

The investigator or a designee from each institution must participate in a regular conference call to update and inform regarding the progress of the trial.

